**Title: Dose of Vestibular Rehabilitation Required for Clinical Improvements in Individuals With Vestibular Hypofunction**

**NCT04851184**

**Date Approved: 11/13/23**

**Protocol and Statistical Analysis Plan.**

**Description:**

When a potential subject is identified, the subject will be screened for appropriateness of inclusion for this study. The screen will include: questions regarding history of concussion, questions related to type of vestibular symptoms (dizziness, room spinning, imbalance, etc.), an oculomotor screen for gaze and spontaneous nystagmus, a Head Impulse Test, and a Dynamic Visual Acuity Test. Subjects will be excluded if they have a gaze nystagmus in room light, a convergence disorder detected with oculomotor screening, or are currently enrolled in vision therapy, as an adjunct treatment. These findings would indicate that the patient's diagnosis falls in a category not included in this study, or that visual disturbances would be a confounding factor during this study. If, following screening, the potential subject is determined to be appropriate for this study, informed consent will be obtained after the potential subject has all their questions answered to their satisfaction.

After informed consent has been obtained from a recruited subject, those with Unilateral Vestibular Hypofunction (UVH) will be asked to perform a 4-week intervention, while those with Bilateral Vestibular Hypofunction (BVH) or those post-concussion will each be asked to perform a 12-week intervention. Those with UVH will undergo a shorter intervention due to strong evidence that neural adaptation occurs much more quickly (usually 4 weeks) than those with BVH and history of concussion. The intervention will consist of physical therapy visits combined with a home program of specific vestibular exercises. Each subject will be asked to attend physical therapy visits at least one time per week throughout the 4- or 12-week period.

Assessments will be performed on all groups and consist of a combination of vestibulo-ocular assessment, balance and clinical functional outcome measures, a survey regarding the usability of the virtual reality device, and surveys of subject satisfaction (see table below). Balance and functional outcome measures will include the Dizziness Handicap Inventory (DHI), Visual Analog Score (VAS) of symptoms, Visual Vertigo Analogue Scale, Functional Gait Assessment (FGA), Activities-Specific Balance Confidence (ABC) Scale, and the modified Clinical Test of Sensory Organization and Balance (CTSIB). Vestibulo-ocular assessment will be conducted using Frenzel goggles and will include tests of: Spontaneous Nystagmus, Gaze-evoked Nystagmus, Smooth Pursuit, Doll's Eyes, Head Impulse, Dynamic Visual Acuity, and Dix-Hallpike. Subjects will also perform the X1 vestibulo-ocular reflex exercise using the virtual reality device for a maximum of 30 seconds in incrementing levels. The X1 involves focusing on a stationary letter while

moving the head back and forth or up and down at approximately 1 cycle per second. If at any point the patient experiences an increase of 3 points on a scale of 0 (no dizziness) to 10 (worst imaginable) of symptoms, exercise in the device will stop. For instance, if a subject begins with a rating of 1/10 dizziness, they are instructed to stop if their symptoms reach a 4/10 or greater. Additionally, at weeks 4, 8 and 12, surveys would ask about patient comfort and level of satisfaction with regards to the intervention protocol. At the conclusion of their participation, subjects will be asked to complete the System Usability Scale to determine the usability of the virtual reality device. On each day of testing, subjects are free to skip any tests or questions they do not want to perform.

Subjects are randomly assigned to the usual rehabilitation or intervention group based on each of the following diagnostic categories: Unilateral Vestibular Hypofunction, Bilateral Vestibular Hypofunction, and post-Concussion. Therefore, there will be a total of three (3) usual rehabilitation and three (3) intervention groups (see table below). Additionally, there will be a seventh group consisting of healthy control subjects that have no history of vestibular symptoms.

Each of the three usual rehabilitation groups will perform usual physical therapy including a home VOR retraining exercise program without the use of the virtual reality headset. The VOR exercise (commonly referred to as the "X1" exercise) will involve holding a piece of paper at arm's length at eye level with an "X" written on the paper. The patient will then rotate their head right and left, reaching 30-45 degrees of excursion in each direction, while attempting to keep their eyes focused on the letter "X". They will then repeat this procedure in the up and down direction. The complexity of the background and duration of exercise will be increased via instruction from the therapist. They will be asked to keep a log of their exercises to assess patient reported compliance. In general, Subjects will be instructed to begin performing the exercises for a duration of 30 seconds at the fastest rate possible so that the 'X' remains in focus and their symptoms are tolerable. As the days progress, Subjects should increase the duration and speed of the exercises as they are able, until they can perform each set for 2 minutes at approximately 1 Hz (1 head shake per second) without any aggravation of symptoms. Once the patient has reached this point, the complexity of exercise background will be increased. Once the background complexity is increased, the patient will be instructed to again start at 30 second exercise bout durations and gradually increase until they are able to achieve 120 seconds without increase in symptoms. Once the patient achieves 120 seconds without symptoms, they will repeat the combination of exercise duration and background complexity increase in the standing position. To perform in a standing position, the patient will be instructed to stand in the corner of a room with a stable chair in front of them to provide a safe environment in which to perform the exercise and by preventing limit chance of falling.

Subjects in the three intervention groups will be asked to perform the same type of exercises as the usual rehabilitation group, but using a virtual reality device that will be issued to the patient for home use. Subjects will use a custom designed program to perform the exercises using a commercially available virtual reality device (no specialized hardware or additions to the commercially available device will be performed). Subjects will be instructed on the first day in how to operate the Virtual Reality Vestibular Rehabilitation (VRVR) program and how to properly perform the exercises. The VRVR device and software will simulate a virtual reality 'room' with an 'X' fixed in front of a wall. Six different background complexities will be offered: 1) plain grey wall, 2) checker board wall, 3) tight houndstooth wall, 4) visual flow from top to bottom, 5) visual flow to the direction of hypofunction, and 6) visual flow moving away from the nose bilaterally. Exercise sessions will start seated upright in a chair and will progress to standing per the home exercise protocol. The system will prompt the patient to begin the exercise and will automatically log the frequency and duration of exercise performed. The system will ask the patient to rate the severity of their symptoms on a 0-10 scale before and after each bout of exercise. Subjects' instruction regarding initial dose and progression will be identical to those given in the usual rehabilitation group. In addition to the general satisfaction survey given to the usual rehabilitation group, Subjects in the intervention group will also be asked to complete a survey regarding comfort, usability, and satisfaction with the VR instrument and with the VRVR software. Subjects will be asked to bring their device with them to their 4 week, 8 week, and 12 weeks appointment to transfer their de-identified data and to insure integrity of the data and device. Subjects will be asked to return the device at the end of the intervention period.

Per patient and therapist discretion, additional physical therapy visits may be scheduled to aid in patient understanding of exercise progression protocol, assess correct performance of exercise (with or without virtual reality device). Non-study related physical therapy visits may be scheduled between sessions in order to address impairments unrelated to vestibulo-ocular deficits. These may include interventions to address musculoskeletal deficits or other balance related impairments. Any additional sessions of physical therapy will be reported in order to determine possible confounding information.

There will be an additional group of healthy control subjects that will be tested for only one day. Healthy subjects will be recruited through flyers, approved email lists, and word of

mouth in the general public. This healthy control group will perform the same tests as the other groups perform on Day 1. This group will be used to compare outcomes of usual rehabilitation and intervention groups, to the function of those without disorders of vestibular function.

Statistical Analysis Plan:

Similarities in subject group characteristics will be determined using a one-way ANOVA. Characteristics will include: Age, height, weight, questionnaire scores, and functional outcome scores. A two-way Repeated-Measures ANOVA will be used for analysis of functional outcomes measures for each assessment time (0,4,8, and 12 weeks) for each group of Unilateral Vestibular Hypofunction, Bilateral Hypofunction Dysfunction, and Post Concussion Syndrome compared to their respective controls. A one-way ANOVA will be used to compare functional outcome measures of all groups on the final day of treatment only to healthy control performance. A multiple regression analysis will be used to determine the relationship between the exercise parameters and changes in outcome measures.

Group	Subgroup	Home Program Intervention	Visits	Test performed by all groups
Unilateral Vestibular Hypofunction	Usual rehabilitation	Usual Physical Therapy with patient self-reported compliance log	1) Initial Evaluation 2) 4-Weeks post	Questionnaires  Dizziness Handicap Inventory Activities-Specific Balance Confidence Scale  Visual Vertigo Analog Scale  Visual Analog Score of symptoms
	Intervention	Home exercises using Virtual Reality Vestibular Rehabilitation	1) Initial Evaluation 2) 4-Weeks post	  Functional Assessment
	Usual rehabilitation	Usual Physical	1) Initial Evaluation	

Bilateral Vestibular Hypofunction		Therapy with patient self- reported compliance log	2) 4-Weeks post  3) 8-Weeks post  4) 12-weeks post	Functional Gait Assessment  modified Clinical Test of Sensory Organization and Balance
	Intervention	Home exercises using Virtual Reality Vestibular Rehabilitation	1) Initial Evaluation  2) 4-Weeks post  3) 8-Weeks post  4) 12-weeks post	Cervical Joint Position Error Test  Vestibulo-ocular assessment using Frenzel goggles:  Spontaneous Nystagmus  Gaze-evoked Nystagmus
Post- Concussion Syndrome	Usual rehabilitation	Usual Physical Therapy with patient self- reported compliance log	1) Initial Evaluation  2) 4-Weeks post  3) 8-Weeks post  4) 12-weeks post	Smooth Pursuit  Doll's Eyes  Head Impulse Test  Dynamic Visual Acuity  Dix-Hallpike.
	Intervention	Home exercises using Virtual Reality Vestibular Rehabilitation	1) Initial Evaluation  2) 4-Weeks post  3) 8-Weeks post  4) 12-weeks post	VRVR Assessment  30 seconds of exercise, incrementing background complexity until an increase of 3/10 symptoms occurs Device

Healthy Control	Control	None	1) Single Visit	Usability System Usability Scale
-----------------	---------	------	-----------------	----------------------------------------------------------

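### No rule covers tests that subjects may skip, so a conventional repeated-measures ANOVA could discard observed scores in the four-visit groups (a precision issue, low severity)

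*Combined protocol and SAP*

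**What the plan says.** The Description section of the combined protocol and SAP lists the outcomes ("Balance and functional outcome measures will include the Dizziness Handicap Inventory (DHI" is how the list opens) and closes its account of the assessments with: "On each day of testing, subjects are free to skip any tests or questions they do not want to perform". The permission applies to every testing day, so it includes baseline.

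The Statistical Analysis Plan section states: "A two-way Repeated-Measures ANOVA will be used for analysis of functional outcomes measures for each assessment time (0,4,8, and 12 weeks", within each diagnostic group and against that group's own controls. It names no analysis set, rule for missing scores, method of fitting or specific contrast.

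The number of visits differs by diagnosis:
- **Bilateral hypofunction and post-concussion:** "those with Bilateral Vestibular Hypofunction (BVH) or those post-concussion will each be asked to perform a 12-week intervention". The table of groups and visits gives them four assessments, the last being "4) 12-weeks post".
- **Unilateral hypofunction:** "those with Unilateral Vestibular Hypofunction (UVH) will be asked to perform a 4-week intervention". The table gives them two assessments.

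Two other analyses also meet skipped tests without a rule. One is a one-way ANOVA comparing "outcome measures of all groups on the final day of treatment only to healthy control performance". The other is described thus: "A multiple regression analysis will be used to determine the relationship between the exercise parameters and changes in outcome measures".

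**The concern.** The plan allows incomplete data by design and then names a method whose usual form needs a complete set of visits. A subject in a four-visit group who declines one test at week 8 may lose the baseline, week-4 and week-12 scores on that outcome as well. The comparison of arms over time would then rest on subjects who completed every visit, with a wider confidence interval than the collected data allow. The plan also leaves the handling of these subjects to be settled after the data have been seen.

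**Working it through.** **Inputs from the documents.** Four visits for bilateral hypofunction and post-concussion and two for unilateral hypofunction (table of groups and visits); any test may be skipped on any testing day (Description); repeated-measures ANOVA with no missing-score rule (Statistical Analysis Plan). The documents give no sample size, skip rate, correlation or power figure, so there is no figure of the plan's own to reproduce.

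**Assumed inputs.** Skip probability p per visit of 2, 5, 10, 15 or 20%; equal correlation rho between a subject's scores, 0.6 in the main case; equal arms; unit variance. The contrast is the arm difference in change from baseline to week 12. It was chosen for illustration, because the SAP names none.

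**Step 1: the mechanism.** A standard repeated-measures ANOVA routine was given 10 subjects with 4 visits each and one of the 40 scores removed. It refused to fit because the data were unbalanced. Listwise deletion then used 36 of the 39 observed scores, so one skipped test cost three scores that had been collected.

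**Step 2: subjects and scores lost.** With independent skipping, the share of subjects complete at four visits is (1 − p)^4. The share of observed scores discarded is 1 − (1 − p)^3. At p = 10% these are 0.90^4 = 66% and 1 − 0.90^3 = 27%.

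**Step 3: width of the confidence interval.** Standard errors below are in SD units and are to be divided by the square root of the number per arm.
- All-visit complete cases: sqrt(4(1 − rho)/(1 − p)^4). At p = 10% and rho = 0.6 this is sqrt(1.6/0.6561) = 1.562.
- Mixed model on all observed scores: from the information matrix summed over all missingness patterns, with separate means for each arm at each visit. At the same values it is 1.353.
- Ratio: 1.562/1.353 = 1.154, or 15% wider.
- Change score on everyone with baseline and week 12: sqrt(1.6/0.81) = 1.405. Ratio to the mixed model: 1.405/1.353 = 1.04.

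| Skip rate per visit | Complete at four visits | Observed scores discarded | All-visit complete cases vs mixed model | Baseline and week-12 change score vs mixed model |
|---|---|---|---|---|
| 2% | 92% | 6% | 1.028 | 1.01 |
| 5% | 81% | 14% | 1.072 | 1.02 |
| 10% | 66% | 27% | 1.154 | 1.04 |
| 15% | 52% | 39% | 1.246 | 1.06 |
| 20% | 41% | 49% | 1.352 | 1.08 |

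The last column equals the one before it times (1 − p), since the change score needs two visits rather than four. Taking rho as 0.4 or 0.8 moves the fourth column by about one percentage point at most.

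**Step 4: the same people skipping repeatedly.** With a within-person skip correlation of 0.2 (beta-binomial), the all-visit complete-case interval is 2/5/10/15/21% wider at the five skip rates. With 0.5 it is 1/2/5/7/10% wider.

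**Step 5: unilateral hypofunction.** With two visits and independent skipping the ratio runs from 1.002 to 1.072 over rho 0.4 to 0.8 and skip rates 2 to 20%, so 0–7% wider.

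**Step 6: bias.** The simulation used 400,000 subjects per arm, correlation 0.6, no arm effect, base skip rate 10% or 20%, and skipping related to the same-day score in one arm only (slope 0.5, 1.0 or 1.5 per SD).
- Baseline never skipped: mixed-model bias about 0.03–0.18 SD, against 0.02–0.10 SD for the complete-case change score.
- Same skipping rule at baseline too: both about 0.

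**The case against.** The strongest reply has four parts.

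1. **The plan does not exclude a fit that keeps partial records.** This stands. The SAP does not say how the ANOVA will be fitted, so a reader may infer, but the documents do not show, that scores will be discarded. The point is that the plan leaves it open.

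2. **The sizes are assumed.** This stands too. The Description gives a permission, not a forecast of skipping. At 2% the loss is small in every case, and it shrinks when the same people skip repeatedly.

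3. **A mixed model is not needed to recover most of the precision.** Largely right for the contrast used here. A change score on everyone with baseline and week 12 comes within 1–8% of the mixed model. The large figures measure deletion across four visits, not skipping as such. The mixed model still keeps subjects who lack one of those two scores and covers all visits in one analysis.

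4. **The mixed model can be the more biased choice.** True in one setting: same-day score-related skipping in one arm, with baseline never skipped. It is not a general result, because the difference disappears when baseline is skipped under the same rule.

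A reader might also infer that the planned comparison is biased. That would need skipping that is related to scores and acts differently by arm and by visit. The documents contain nothing on this.

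**Conclusion.** The point holds as a low-severity matter of precision, one to consider rather than a flaw that undermines the trial. What is certain is that tests may be skipped on any testing day and that no rule for skipped tests is given. That a conventional repeated-measures ANOVA drops incomplete subjects is a property of the method. How much is lost is unknown. Under independent skipping of 2–20% per visit and correlation 0.6, an all-visit complete-case analysis of bilateral hypofunction or post-concussion gives an interval 3–35% wider than a mixed model. The loss is less when skipping clusters within people, and 0–7% for unilateral hypofunction. The upper figures should not be read as a prediction for this trial.

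**What to change.** For bilateral hypofunction and post-concussion, replace the repeated-measures ANOVA in the Statistical Analysis Plan with a linear mixed model fitted by REML. Specify:
- the same effects (arm, visit and arm-by-visit), on all observed scores, with subjects in the arm to which they were randomised;
- baseline kept as a response, so that a skipped baseline does not remove the subject;
- unstructured covariance, with compound symmetry prespecified as the fallback if the model does not converge;
- the week-12 arm contrast in change from baseline, reported with its confidence interval.

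Unilateral hypofunction may use the two-visit version for a small gain.

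**Cost.** SAP wording and standard software; no new assessments and no change to the subjects' freedom to skip. With complete, balanced data the compound-symmetry version gives the same arm-by-visit test as the planned ANOVA. The price is reliance on missing-at-random. A simple sensitivity analysis in which skipped scores are set somewhat worse, in one arm and then in both, is therefore sensible but optional. So are recording the reason for each skip and stating how questionnaires with skipped items are scored.

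**What it does not reach.** The final-day comparison with healthy controls and the regression on changes remain exposed to skipped tests. Reporting how many subjects per group have the values needed would make that visible.

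### The one-way ANOVA for group similarity cannot show balance between randomised arms, and the repeated-measures ANOVA names no baseline covariate and no term that tests the arms

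*Combined protocol and SAP*

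**What the plan says.** The Statistical Analysis Plan section opens with the sentence "Similarities in subject group characteristics will be determined using a one-way ANOVA". The variables are listed next: "Characteristics will include: Age, height, weight, questionnaire scores, and functional outcome scores". It does not say which groups enter, at what alpha, with what follow-up contrasts, or what is done with the result. No equivalence margin and no sample size are given.

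The Description section sets out the design: "Subjects are randomly assigned to the usual rehabilitation or intervention group based on each of the following diagnostic categories", the categories being unilateral vestibular hypofunction (UVH), bilateral vestibular hypofunction (BVH) and post-concussion. It adds that "there will be a total of three (3) usual rehabilitation and three (3) intervention groups", and then: "Additionally, there will be a seventh group consisting of healthy control subjects that have no history of vestibular symptoms". On their data it says: "This healthy control group will perform the same tests as the other groups perform on Day 1". Healthy controls are named in the later sentence on the final-day ANOVA, but not in the similarity sentence.

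For the arm comparison, the Statistical Analysis Plan section gives a two-way repeated-measures ANOVA over weeks 0, 4, 8 and 12, each diagnostic group against its own controls. No covariate is named, nor which term (group, or group by time) tests the arms. The visit table gives UVH only the initial evaluation and week 4; the other two diagnoses have all four visits.

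**The concern.** There are two separate gaps.

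First, the inference in the similarity sentence runs the wrong way. Failing to reject equality is not evidence of equality, least of all in small groups. The contrast of interest is between two randomised arms within one diagnosis, whereas a one-way test over several groups pools that contrast with differences between diagnoses. A report could say the groups differ when every randomised pair is balanced, or say they are similar when one pair is visibly apart.

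Second, the sentence that does compare the arms makes less use of the baseline score than it could. With week 0 as a response level, the group main effect averages in a value measured before treatment. The group-by-time term compares change, which is noisier than baseline adjustment and over-corrects when the arms happen to start apart. Because the plan does not name the term, the reader cannot tell which of these applies.

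At stake are an unsupported statement about baseline, lost precision, and an estimate that is off in those trials where chance leaves the arms unequal at the start.

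**Working it through.** **Inputs.** From the documents: six patient groups in three randomised pairs, a seventh healthy group with Day 1 data, week 0 as a level of the repeated-measures ANOVA. Not stated, so assumed: equal groups of 10 to 30, SD = 1, two-sided alpha 0.05, baseline-to-follow-up correlation r of 0.3 to 0.7. The plan has no figure of its own to reproduce.

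**1. What it would take to show similarity.** Two one-sided tests with a margin of 0.5 SD, 80% power and a true difference of 0 need n per arm = 2 × ((1.645 + 1.282)/0.5)² ≈ 68.5, so 69. The margin is an assumption; the plan sets none.

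**2. The six-group test rejects with balanced arms.** Put the diagnosis means at −0.5, 0 and +0.5 SD, with both arms of each diagnosis equal. The noncentrality is n × Σ(mean − grand mean)² = n × (4 × 0.25) = n. The rejection probability is 0.63 (n = 10), 0.84 (15), 0.94 (20) and 0.99 (30). Healthy controls play no part in this.

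**3. If healthy controls are included.** With six equal patient groups and healthy controls D SD away, the noncentrality is n × D² × 6/7. This bears on symptom and functional scores, not on age, height or weight.

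| n per group | D = 1.0 | D = 1.5 | D = 2.0 |
|---|---|---|---|
| 10 | 0.52 | 0.90 | 0.995 |
| 15 | 0.74 | 0.99 | 1.00 |
| 30 | 0.98 | 1.00 | 1.00 |

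**4. What observed gap passes as similar.** Suppose one pair is observed d SD apart and the other four means lie at its midpoint. Then F = (n × d²/2)/5, so the largest unflagged gap is d = √(10 × Fcrit/n). For n = 10, Fcrit(5, 54) = 2.386 and d = 1.54 SD. For n = 30, Fcrit(5, 174) = 2.266 and d = 0.87 SD.

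**5. How often chance produces a gap.** P(|gap| ≥ g) = 2 × [1 − Φ(g/√(2/n))] for a given pair and variable. For g = 0.5 SD it is 0.26 (n = 10), 0.17 (15), 0.11 (20) and 0.05 (30). For g = 0.8 SD it is 0.07 (n = 10) and 0.01 (n = 20).

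**6. Precision, one baseline/follow-up pair.** Apart from the common factor 2/n, the variance of the arm contrast is 2(1 − r) for change and 1 − r² for ANCOVA. The ratio is (1 + r)/2 = 0.65, 0.75 and 0.85 for r = 0.3, 0.5 and 0.7, a reduction of 35%, 25% and 15%.

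**7. Dilution of the group main effect.** With two visits, a true effect of 0.8 SD at follow-up appears as 0.8/2 = 0.40. With four visits and a constant effect after week 0, it appears as 0.8 × 3/4 = 0.60.

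**8. A fixed baseline gap of 0.5 SD and no treatment effect, two visits.** Expected estimates are:
- main effect: 0.5 × (1 + r)/2 = +0.325, +0.375, +0.425 for r = 0.3, 0.5, 0.7;
- change: −0.5 × (1 − r) = −0.35, −0.25, −0.15;
- ANCOVA: 0.

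Simulation with 4,000 trials per setting agrees. At n = 30 per arm and r = 0.5:

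| | Main effect | Group by time | ANCOVA |
|---|---|---|---|
| Power, effect 0.8 SD | 0.43 | 0.87 | 0.94 |
| False rejection, given the 0.5 SD gap | 0.28 | 0.12 | 0.05 |

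With no gap imposed and no effect, rejection was 0.040 to 0.054 for all three methods over n = 15 and 30 and all r. Averaged over randomisation, none of them inflates the type I error.

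**The case against.** Several stronger readings are tempting, and the documents do not carry them.

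- *A reader might infer that the test rejects by design because healthy controls are in it.* The similarity sentence does not say so, and healthy controls are named only in the final-day ANOVA. If they are included, rejection depends on an unknown gap (0.52 at 1 SD, 0.995 at 2 SD, n = 10) and does not extend to age, height or weight.
- *A reader might calculate that an arm shifted by 0.8 SD is missed in 65% of trials at n = 10 and 31% at n = 20.* Those figures assume a population shift between paired arms, which randomisation within diagnosis rules out. A chance gap that large in a given pair has probability of about 7% and 1%.
- *A reader might conclude that the arm comparison ignores baseline.* Week 0 is a level of the repeated-measures ANOVA, so the group-by-time term already compares change from baseline. It is not covariate-adjusted, which is a narrower criticism.
- *A reader might blame the similarity test for the missing adjustment.* The plan ties no action to that test; the gap lies in the repeated-measures sentence.

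It is also fair to say that (1 + r)/2 describes a single baseline/follow-up pair. It fits UVH directly, but not the four-visit analyses, where the group-by-time test has several degrees of freedom.

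These objections narrow the point. They do not rescue the inference from non-significance to similarity, and they do not supply the missing term or covariate.

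**Conclusion.** The point holds in two parts. The similarity test cannot support the conclusion it is meant to give, which needs no assumed numbers. Its failure to describe the randomised pairs does not depend on healthy controls: differences between diagnoses suffice (rejection of 0.63 to 0.99 with balanced arms, assuming diagnoses 0.5 SD apart and n of 10 to 30).

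The arm comparison leaves precision unused and its test term undefined. For one baseline/follow-up pair, baseline adjustment cuts variance by 15-35% against change at assumed r of 0.7 to 0.3. The bias is conditional on a chance imbalance and is not an inflation of the overall error rate. All sizes rest on assumed n, SD, alpha and r, because the plan gives none. The defect does not make the trial unusable, but it is well worth correcting.

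**What to change.** Change two sentences in the Statistical Analysis Plan section; changing only the first would leave the baseline score as both response and covariate.

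1. Replace the similarity sentence with: *Baseline characteristics will be summarised by randomised arm within each diagnosis (mean, SD, standardised difference), without hypothesis tests. Healthy controls will be shown in a separate column.*
2. Replace the repeated-measures sentence with: *Within each diagnosis, the randomised arms will be compared on post-baseline scores (week 4 for UVH; weeks 4, 8 and 12 for BVH and post-concussion) by ANCOVA or a repeated-measures mixed model. The week 0 score of that outcome will be a covariate and not a response level, whatever the observed balance.* State also which arm contrast is the one to be reported.

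Other covariates such as age are not required by this point; nothing in the documents identifies age as prognostic.

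The cost is wording and one degree of freedom per model. Visits, tests and data collection do not change, since the scores are already taken at the initial evaluation. Subjects may skip tests, so the text should say how a missing week 0 score is handled.

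### The arm comparison does not name the term or visit that tests treatment and does not adjust for the week-0 score; one named, baseline-adjusted contrast per diagnosis would usually be more precise, using data already scheduled

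*Combined protocol and SAP*

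**What the plan says.** Allocation is randomised within diagnosis (Description): "Subjects are randomly assigned to the usual rehabilitation or intervention group based on each of the following diagnostic categories".

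The whole analysis of the randomised arms is one sentence of the Statistical Analysis Plan section: "A two-way Repeated-Measures ANOVA will be used for analysis of functional outcomes measures for each assessment time (0,4,8, and 12 weeks" and, after the bracket closes, "for each group of Unilateral Vestibular Hypofunction, Bilateral Hypofunction Dysfunction, and Post Concussion Syndrome compared to their respective controls". Arm and visit are therefore the two factors, and week 0 is one of the visits. No covariate is listed, and no term, visit or contrast is singled out as the treatment test.

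The follow-up schedules differ. The Description gives UVH subjects 4 weeks of treatment; for the other two diagnoses it states that "those with Bilateral Vestibular Hypofunction (BVH) or those post-concussion will each be asked to perform a 12-week intervention". The visit table agrees: the UVH rows read "1) Initial Evaluation 2) 4-Weeks post", and the bilateral (BVH) and post-concussion rows add weeks 8 and 12.

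Two other sentences of the same section bear on the point. Change from baseline appears only in the dose regression, on the "relationship between the exercise parameters and changes in outcome measures". The comparison with healthy controls is to "compare functional outcome measures of all groups on the final day of treatment only". The Description lets subjects decline any test on any day, and the analysis section gives no rule for the gaps.

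**The concern.** A two-way repeated-measures ANOVA gives a group main effect and a group-by-time interaction. Because week 0 precedes treatment, the two answer different questions: the main effect averages treated visits with an untreated one, while the interaction asks whether the arms diverge. A reader cannot tell from the plan which result will be reported as the effect of the virtual-reality programme.

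The second matter is efficiency. Randomised arms share the same expected week-0 score. Treating that score as an outcome spends information on a difference known to be zero in expectation; using it as a covariate usually gives a tighter estimate from the same data. What is at stake is the precision and pre-specification of the three randomised comparisons, not the validity of the interaction test.

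**Working it through.** **Inputs from the plan.** Randomisation within diagnosis; UVH at weeks 0 and 4; BVH and post-concussion at weeks 0, 4, 8 and 12. The plan states no sample size, alpha, power, effect size, SD or correlation, so it has no figure to reproduce.

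**Assumed for illustration.** Two-sided 5%, n per arm with equal arms, SD 1 at every visit, the same correlation ρ between any two visits, and a true final-visit difference of 0.8 SD.

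**UVH, two visits.** The group-by-time F is the square of the t statistic on the change score (checked on simulated data: 1.2313 for both). In units of 2·SD²/n, the large-sample variance of the arm difference is:
- change score: 2(1−ρ)
- ANCOVA: 1−ρ² = (1−ρ)(1+ρ)
- ratio of change score to ANCOVA: 2/(1+ρ), that is 1.33, 1.25 and 1.18 at ρ 0.5, 0.6 and 0.7.

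The main effect averages a difference of 0 with one of 0.8, giving 0.4, which is half the effect.

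At n = 20 and ρ = 0.6, √(2/20) = 0.316. The ratios of effect to standard error are:
- change score: 0.8/(√0.8 × 0.316) = 2.83
- ANCOVA: 0.8/(√0.64 × 0.316) = 3.16
- main effect: 0.4/(√0.8 × 0.316) = 1.41.

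Power by noncentral t (ANCOVA with 2n−3 df, averaged over the chance baseline difference), 20 per arm:

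| ρ | main effect | group-by-time | ANCOVA |
|---|---|---|---|
| 0.5 | 30% | 69% | 80% |
| 0.6 | 28% | 79% | 86% |
| 0.7 | 27% | 89% | 92.5% |

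For 80% power, group-by-time needs 26, 21 and 16 per arm at these correlations, and ANCOVA 20, 18 and 15. At ρ 0.8 both need 11.

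**BVH and post-concussion, four visits.** The interaction is a 3-df F test on 3 and 3(2n−2) df, with noncentrality (n/2)·Σ(eⱼ−ē)²/(1−ρ), where eⱼ is the arm difference at visit j. At n = 20 and ρ = 0.6:
- linear build-up (0, 1/3, 2/3, 1 times 0.8): Σ = 0.64 × 0.556 = 0.356, noncentrality 10 × 0.356/0.4 = 8.9
- constant from week 4 (0, 1, 1, 1 times 0.8): Σ = 0.64 × 0.75 = 0.48, noncentrality 10 × 0.48/0.4 = 12.

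Power, 20 per arm:

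| ρ | 3-df, linear | 3-df, constant | week-12 ANCOVA |
|---|---|---|---|
| 0.5 | 58% | 73% | 80% |
| 0.6 | 69% | 83% | 86% |
| 0.7 | 82% | 92.5% | 92.5% |
| 0.8 | 95% | 98.9% | 98.1% |

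The main effect here would show (0 + 1/3 + 2/3 + 1)/4 = 1/2 of the week-12 effect if linear and 3/4 if constant.

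**Very small arms.** At 5 per arm and ρ 0.8 with two visits, the change score has 42% and ANCOVA 40%. At 10 per arm and ρ 0.8 with four visits and a constant effect, the 3-df test has 81% and week-12 ANCOVA 78%. At ρ 0.6 or below, ANCOVA led in every case calculated at 0.8 SD.

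**The case against.** Several objections have force.

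- **The comparison is named.** Setting each diagnosis against its own controls over the visits makes group-by-time the ordinary reading. This stands. A reader might infer that the plan omits the treatment comparison or that its test is invalid; the documents support neither. What is missing is the designated term and visit.
- **No change-score comparison of arms is planned.** This also stands. The equivalence is exact only for UVH; in the other two diagnoses the comparator is a 3-df test that a week-12 contrast does not always beat.
- **The gain rests on inputs that the plan does not give.** True, and it can reverse slightly, as the small-arm figures show. Baseline adjustment should not be described as better without condition.
- **Reading the main effect, or counting either term, is hypothetical.** If either term at p<0.05 counted as success, the false-positive chance per measure would be 1−0.95² = 9.75%. The plan does not say it would do this, so the figure is a reason to name the term, not an error rate of the plan.
- **Skipped tests.** With 10% of each later test skipped at random and listwise deletion (both assumed), simulated power under a linear effect is 52% for the ANOVA and 80% for a mixed-model week-12 contrast. It is tempting to credit the 28 points to missing-data handling. With nothing missing the figures are 67% and 86%, so 19 of the 28 points come from the choice of contrast. If the same subjects skip every later test, the mixed model recovers nothing.
- **Multiplicity remains.** The Description lists six balance and functional measures; over three diagnoses, one contrast each still makes 6 × 3 = 18 tests. The fix does not address this.

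**Conclusion.** The point holds as a matter of pre-specification and efficiency. The plan should say which term and visit test treatment, and it leaves week-0 information unused as a covariate.

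In UVH the large-sample gain is certain in direction for any ρ below 1, but its size depends on ρ: the ANCOVA variance is 75% to 85% of the planned test's for ρ 0.5 to 0.7, and power rises by about 11, 7 and 4 points in the illustration. In BVH and post-concussion, a baseline-adjusted week-12 contrast is clearly stronger if the effect builds up (17 points at ρ 0.6). If the effect is constant from week 4, it is a little stronger at ρ 0.6 (3 points) and about equal or slightly weaker from ρ about 0.7. All power figures rest on the assumed 0.8 SD effect, arm size and equal-correlation structure.

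The list of four times for all three diagnoses conflicts in wording with the two UVH visits. A reader might infer that UVH is to be analysed at weeks 8 and 12, but the Description and the visit table both fix weeks 0 and 4, so this needs reconciling and changes no result.

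**What to change.** For each functional outcome, name one arm contrast in advance, adjusted for the week-0 score:

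- **UVH:** ANCOVA of the week-4 score on arm and baseline, with weeks 0 and 4 stated as the only analysis times.
- **BVH and post-concussion:** a mixed model on weeks 4, 8 and 12 with arm, visit, arm-by-visit and baseline, a small-sample degrees-of-freedom correction such as Kenward-Roger, and the week-12 arm difference as the treatment contrast. This matches the plan's own use of the final treatment day for the healthy-control comparison. The model keeps subjects who skip some later tests, under a missing-at-random assumption that should be stated. Say also how a skipped baseline test is handled.

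If the ANOVA is kept, the minimum is to name group-by-time as the treatment test and state how skipped tests are handled.

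Cost: a few sentences in the analysis plan, with standard software and no new visits, data or patients. Downside: the baseline term spends one degree of freedom, with a small possible loss of power in very small arms, or with an early constant effect and high ρ. Multiplicity across outcomes needs separate treatment.
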